6.5.5 Disposal and destruction

The drug supply can be destroyed at the local Novartis facility, Drug Supply group or third party, as appropriate.

7 Visit schedule and assessments

7.1 Study flow and visit schedule

Table 7-1 lists all of the assessments and indicates with an “X”, the visits when they are performed. All data obtained from these assessments must be supported in the patient’s source documentation. The table indicates which assessments produce data to be entered into the database (D) or remain in source documents only (S) (“Category” column).

Table 7-1 Visit evaluation schedule

	Category	Reference to Section	Screening	Baseline	Study period													Study Phase Completion	Study Completion
					1	2	3	4	5	6	7	8	9	10	11	12	13, 14,.... ^a		
Visit Number																		776	777
Study Week	7.1.2.	-3 to 0	0	1	2	3	4	5	6	7	8	12	16	20	24	36	48, 60,.... ^a	Last dose	Last dose + 4
Study days	7.1.2.	-21 to -1	0	7	14	21	28	56	84	112	140	168	252	336, 420, ^a			Last dose	Last dose + 28	
Obtain Informed Consent	D		X																
Demography	D	7.1.1.2.	X																
Inclusion/exclusion criteria	D		X																
Complete Inclusion / Exclusion Criteria Checklist			X																
Relevant medical history/current medical conditions	D		X																
Physical examination	S	7.2.2.1.	X	X	X	X	X	X	X	X	X	X	X	X	X	X	X	X	
Karnofsky performance status	D	7.2.2.3.	X							X			X	X	X	X			X
Height	D	7.2.2.1.	X																
Vital signs	D	7.2.2.2.	X	X	X	X	X	X	X	X	X	X	X	X	X	X	X	X	X
Gallbladder Ultrasound	D	7.2.2.6.	X						X			X	X	X	X	X ^b			X
Hematology, GH, IGF-1	D	7.2.2.4.1, 7.2.2.4.3.	X					X	X	X	X	X	X	X	X	X ^b			X
Free T4, TSH	D	7.2.2.4.3.	X						X			X		X		X ^b			X
Blood Chemistry (including Total proteins, amylase, lipase, total cholesterol (TC), LDL-cholesterol, triglycerides, sodium, potassium, magnesium, urea, serum creatinine, creatinine clearance)	D	7.2.2.4.3.	X					X	X	X	X	X	X	X	X	X			X
LFT (ALT, AST, total bilirubin, Albumin, ALP, and GGT)	D	7.2.2.4.3.	X	X	X	X		X	X	X	X	X	X	X	X	X			X

	Category	Reference to Section	Screening	Baseline	Study period													Study Phase Completion	Study Completion
					1	2	3	4	5	6	7	8	9	10	11	12	13, 14,... ^a		
Visit Number					1	2	3	4	5	6	7	8	9	10	11	12	13, 14,... ^a	776	777
Study Week	7.1.2.	-3 to 0	0	1	2	3	4	8	12	16	20	24	36	48, 60,... ^a			Last dose	Last dose + 4	
Study days	7.1.2.	-21 to -1	0	7	14	21	28	56	84	112	140	168	252	336, 420, ^a			Last dose	Last dose + 28	
Coagulation (PT, INR)	D	7.2.2.4.2.	X	X	X	X		X	X	X			X	X	X	X	X	X	
Fasting Blood Glucose	D	7.2.2.4.3.	X		X	X	X	X	X	X	X	X	X	X	X	X	X	X	
Fasting Insulin	D	7.2.2.4.3.	X		X		X	X	X	X	X	X	X	X	X	X	X	X	
HbA _{1c}	D	7.2.2.4.3.	X				X		X			X	X	X	X	X	X	X	
Vitamin B12	D	7.2.2.4.3.	X					X			X		X					X	
Urinary free cortisol and urine creatinine	D	7.2.1.1.1.	X					X	X	X	X	X	X	X	X	X	X	X	
Serum cortisol	D	7.2.1.1.2.	X			X		X	X	X	X	X	X	X	X	X	X	X	
Plasma ACTH	D	7.2.1.1.2.	X		X		X	X	X	X	X	X	X	X	X	X	X	X	
HbsAg and anti-HCV	D	7.2.2.4.6.	X																
Signs and symptoms of Cushing's disease	D	7.2.1.1.3.	X	X	X	X	X	X	X	X	X	X	X	X	X	X	X	X	
Cushing's syndrome HRQoL and WPAI-GH questionnaire	D	7.2.1.1.4 7.2.1.1.5.		X				X		X			X	X	X	X	X	X	
Urinalysis	D	7.2.2.4.4.	X						X			X		X	X	X ^b	X	X	
Serum Pregnancy test	D	7.2.2.4.5.	X							X					X	X	X	X	
ECG	D	7.2.2.5.1.	X	X	X	X	X	X	X	X	X	X	X	X	X	X	X	X	
Adverse events	D	8.1.													Continuously				
Prior/Concomitant medications	D	6.3.	X												Continuously				
Drug administration	D	6.1.													Continuously				
Study phase completion record	D	7.1.3.															X		
Study completion record	D	7.1.4.																X	

	Category	Reference to Section	Screening	Baseline	Study period													Study Phase Completion	Study Completion
					1	2	3	4	5	6	7	8	9	10	11	12	13, 14,... ^a		
Visit Number																		776	777
Study Week		7.1.2.	-3 to 0	0	1	2	3	4	8	12	16	20	24	36			48, 60,... ^a	Last dose	Last dose + 4
Study days		7.1.2.	-21 to -1	0	7	14	21	28	56	84	112	140	168	252	336, 420, ^a			Last dose	Last dose + 28

^a One visit every 12 weeks/84 days until patients are transitioned to commercial pasireotide or until 31 December 2015 (until 31 December 2016 for sites in South Korea and Brazil), whichever comes first

^b To be done every 24 weeks after visit 13

D Data/assessments to be entered in the database

S Data/assessments that remain in source documents only, not to be recorded on CRF

7.1.1 Screening

After the informed consent is obtained, screening evaluations will be performed to assess eligibility for study entry prior to administration of any study drug (Week -3 to 0).

Informed consent must be obtained before starting the washout periods for the drugs indicated in the protocol. The washout period for the drugs indicated in the inclusion criteria need to be completed before urine, blood and saliva collections at screening are started.

Enrollment and eligibility confirmation

In order to determine and confirm the eligibility of the patient, when all screening procedures are complete, a key eligibility checklist must be completed manually by the investigator or designee prior to receiving the first dose. After the eligibility has been checked and the patient is confirmed as eligible for the trial, the patient can then be enrolled into the trial. This checklist must be submitted to the sponsor for approval prior to study enrollment.

7.1.1.1 Information to be collected on screening failures

Patients who sign an informed consent but fail to be started on treatment for any reason will be considered a screen failure. The reason for not being started on treatment will be entered on the Screening Log Page. The demographic information, must also be completed for Screen Failure patients. No other data will be entered into the clinical database for patients who are screen failures, unless the patient experienced a Serious Adverse Event during the Screening Phase (see [Section 8](#) for SAE reporting details).

7.1.1.2 Patient demographics and other baseline characteristics

Standard demographic information and medical history will be collected at visit 1. Cushing's disease history and DM history together with the medication/treatment used will be collected.

7.1.2 Treatment period

Patients will be treated until the drug is approved for commercial use and reimbursed in each respective country or until 31 December 2015 (until 31 December 2016 for sites in South Korea and Brazil), whichever occurs first.

Patients who are transitioned to commercial pasireotide s.c. will be considered as completed as per protocol requirements (refer to [Section 6.1.2](#)).

All visits should be performed on the indicated days. Should this not be possible, the following visit windows apply: +/- 2 days from visit 3 to 11 and +/- 5 days from visit 12 onwards. The Study Phase Completion visit has to be performed on the day of the last study drug administration (+ 5 days). The Study Completion visit has to be performed 28 days (+/- 5 days) after the patient received the last pasireotide s.c. dose.

7.1.3 Study phase completion visit, including premature withdrawal and study discontinuation visit

Patients who permanently discontinue the study drug should be considered prematurely discontinued from the study. Patients will have to perform a study phase completion

evaluation on the day of the last study drug administration (refer to Study Phase Completion evaluation in [Table 7-1](#)).

If a withdrawal occurs, or if the patient fails to return for visits, the investigator must determine the primary reason for a patient's premature withdrawal from the study and record this information on the Study Phase Completion CRF page. If patients refuse to return for these visits or are unable to do so, every effort should be made to contact them.

Patients who complete the study because they are transitioned to commercial pasireotide or patients who are treated until 31 December 2015 (until 31 December 2016 for sites in South Korea and Brazil) will have to perform a study phase completion evaluation on the day of the last study drug administration (refer to Study Phase Completion evaluation in [Table 7-1](#)). A Study Phase Completion CRF page has to be completed.

7.1.3.1 Criteria for premature patient withdrawal

Patients **may** voluntarily withdraw from the study or be dropped from it at the discretion of the investigator at any time.

Patients **must** be withdrawn from the study if any of the following occurs:

- Patients experiencing unacceptable drug-related toxicity (as described in [Table 6-1](#))
- Uncontrolled diabetes mellitus (DM), consistently high capillary glucose values in excess of 275 mg/dL (15.5 mmol/L), FPG \geq 240 mg/dL (13.3 mmol/L) or HbA_{1c} value \geq 10 % despite prior appropriate management and prior dose adjustment of the study drug,
- Patients experiencing adverse events in QTc:
 - a confirmed QTcF $>$ 480 msec and discontinuation recommended by a cardiologist, or
 - Mean QTcF $>$ 500 msec measured by triplicate ECGs and confirmed by a cardiologist
 - Significant arrhythmia findings from Holter monitoring such as:
 1. Any ventricular or supra-ventricular tachyarrhythmia associated with symptoms of hemodynamic compromise
 2. Sustained ventricular tachycardia ($>$ 30 sec) irrespective of symptoms
 3. Recurrent non-sustained VT (\geq 3 beats) during any 24-hour monitoring period
 4. Torsades de Pointes (TdP)
 5. Cardiac arrest
 6. Pause $>$ 5 seconds
 7. Second or third degree AV block
 - New occurrence of clinically significant/symptomatic bradycardia, or
 - Increased risk of QT prolongation by use of medications with known risk of TdP, or
 - Hypokalemia ($<$ 3.5 mmol/L) or hypomagnesaemia ($<$ 0.5 mmol/L) confirmed by repeat testing that is either a new finding or accompanied by vomiting or diarrhea and not corrected by treatment.
- Evidence of hypoadrenalinism: defined as an early morning (between 8 and 10 am) serum cortisol $<$ 3 μ g/dL and a mean 24h-UFC measurement $<$ LLN or symptoms suggestive of

hypoadrenalinism (e.g. postural hypotension, nausea, and abdominal pain) in association with a mean 24h-UFC measurement < LLN, which persist after drug dose adjustment

- Lack of efficacy: consistently elevated mean 24h-UFC level and lack of clinical benefit after ≥ 3 months treatment
- Pregnancy
- Patient experiencing
 - ALT or AST $> 3 \times$ ULN and Total Bilirubin $\geq 2 \times$ ULN and ALP $< 2 \times$ ULN
 - ALT or AST $> 5 \times$ ULN and $\leq 8 \times$ ULN persistent for more than 2 weeks
 - ALT or AST $> 8 \times$ ULN

If any of those 3 discontinuation criteria are met, study medication should be discontinued immediately. In addition, proper safety follow-up management should be performed as outlined in [Section 6.2.1.1](#). Re-challenge of study medication is prohibited once discontinuation criteria are met.

If such withdrawal occurs, or if the patient fails to return for visits, the investigator must determine the primary reason for a patient's premature withdrawal from the study and record this information on the Study Completion CRF page. Patients may be withdrawn from the study prematurely for one of the following reasons:

[figure not shown]
- Adverse event(s)
- Abnormal laboratory value(s)
- Abnormal test procedure result(s)
- Protocol violation
- Subject withdrew consent
- Lost to follow-up
- Administrative problems
- Death

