The principal investigator is to educate the patient on the signs and symptoms of hyperglycemia. In addition to the laboratory evaluation of blood glucose level at the regular scheduled visits ([Table 7-1](#)), patients are asked to self-monitor their blood glucose using a home glucometer provided by Novartis at least 3 times per week for the first month of pasireotide treatment. If the patient does NOT have any fasting values above 100mg/dL, monitoring can be decreased to at least 2 times per week for months 2 and 3 and 1 time every 2 weeks for months 4 through 7. If glucose levels remain normal (below 100mg/dL), monitoring is at the investigator's discretion after month 7. If any values are observed above 100 mg/dL, the guidelines in figure below are to be followed. These guidelines are based on the current recommendations from the 2012 ADA and EASD aiming at a glycemic treatment goal of FPG <130 mg/dL (<7.2 mmol/L). Appropriate actions such as initiation of anti-hyperglycemic therapy (and referral to diabetes specialist) are to be taken by the investigator as outlined on [Figure 6-1](#). If fasting blood glucose values dictate initiation of anti-hyperglycemic treatment (i.e., confirmed >130 mg/dL by self-monitoring), a fasting plasma glucose sample using the local laboratory is to be collected prior to initiation of anti-hyperglycemic treatment. If a patient has a dose increase, monitoring for hyperglycemia should follow the recommendations for the first month of treatment and continue as presented above for subsequent months.

It is recommended that the patients be encouraged to keep a diary for their blood glucose for appropriate management throughout the study and present the collected data to their physician/diabetes specialist for evaluation. This data will not be collected by the sponsor.

In addition to self-monitoring, fasting plasma glucose and HbA1c will be collected at study visits per [Table 7-1](#). Close and frequent monitoring of blood glucose is needed during pasireotide treatment. Intervention for hyperglycemia is to be implemented in any patient meeting any of the following criteria: FPG > 130 mg/dL or HbA1c \geq 6.5 %.

Patients with FPG > 160 mg/dL or HbA1c > 7.5% despite adjustment of antidiabetic therapy should be referred to a diabetes specialist (or earlier per investigator's judgment).

Figure 6-1 Fasting self-monitoring blood glucose (SMBG) guidelines

[figure not shown]
QT prolongation:

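### The capillary glucose limit for mandatory withdrawal, 275 mg/dL (15.5 mmol/L), states two slightly different limits

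*Protocol*

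**What the plan says.** Protocol Section 7.1.3.1 lists the events after which patients must be "withdrawn from the study if any of the following occurs". The bullet on uncontrolled diabetes gives three alternative glycaemic triggers: "consistently high capillary glucose values in excess of 275 mg/dL (15.5 mmol/L"), fasting plasma glucose (FPG) at or above "240 mg/dL (13.3 mmol/L"), and HbA1c of 10% or more. The bullet carries the qualifier "despite prior appropriate management and prior dose adjustment of the study drug".

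One other glucose limit in the readable text is given in both units. It is the treatment goal in Section 6.2.1.1 (Monitoring of blood glucose): "FPG <130 mg/dL (<7.2 mmol/L"). The remaining glucose limits in that section, such as 100 and 160 mg/dL, appear in mg/dL only.

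The capillary readings that patients take at home come from self-monitoring "using a home glucometer provided by Novartis at least 3 times per week for the first month of pasireotide treatment", and less often afterwards if fasting values stay normal. Neither document states the meter's display unit or says which unit governs when the two figures differ. The SAP does not use the capillary limit.

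**The concern.** A limit given in two units should be one limit. The ratio of mg/dL to mmol/L for glucose is a constant, so every such pair in the protocol should give the same ratio up to rounding. The two FPG pairs agree with each other and the capillary pair does not, although one of those FPG pairs sits in the same bullet.

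The figure belongs to a rule that obliges the investigator to withdraw the patient, in a multi-national trial of a drug for which hyperglycaemia is a leading known risk. Protocol Section 1.2.2 reports that 70% of patients in the earlier phase III study had at least one hyperglycaemia-related adverse event. A patient whose capillary values stay between 275 and about 280 mg/dL exceeds the limit for an investigator who reads mg/dL but not for one who reads mmol/L. The capillary trigger stands apart from the FPG and HbA1c triggers and is not restricted to fasting readings, so the other two need not catch the same patient.

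**Working it through.** **Inputs.** Three pairs, all from the protocol. Write f for the conversion factor, f = (mg/dL) / (mmol/L). Each mmol/L value is given to one decimal, so its unrounded value may lie up to 0.05 either side. The mg/dL values are taken as stated.

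| Limit | Section | mg/dL | mmol/L | f as stated | f allowing for rounding |
|---|---|---|---|---|---|
| FPG treatment goal | 6.2.1.1 | 130 | 7.2 | 18.06 | 130/7.25 = 17.931 to 130/7.15 = 18.182 |
| FPG withdrawal limit | 7.1.3.1 | 240 | 13.3 | 18.05 | 240/13.35 = 17.978 to 240/13.25 = 18.113 |
| Capillary withdrawal limit | 7.1.3.1 | 275 | 15.5 | 17.74 | 275/15.55 = 17.685 to 275/15.45 = 17.799 |

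**Step 1: the protocol's own factor.** Both FPG pairs hold for any f from 17.978 to 18.113, the overlap of their two ranges.

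**Step 2: can the capillary pair share it?** The largest f that the capillary pair allows is 17.799, below the smallest value allowed by the other two, 17.978. The ranges do not overlap, so rounding of the mmol/L values does not explain the difference.

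**Step 3: what each figure should be.**
- 275 mg/dL converts to 275/18.113 = 15.18 up to 275/17.978 = 15.30 mmol/L, against the stated 15.5.
- 15.5 mmol/L converts to 15.5 × 17.978 = 278.7 up to 15.5 × 18.113 = 280.8 mg/dL, against the stated 275.

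**Step 4: size of the gap.**
- In mg/dL: 278.65 − 275 = 3.65 up to 280.75 − 275 = 5.75.
- As a share of the limit: 3.65/275 = 1.33% up to 5.75/275 = 2.09%.
- In mmol/L: 15.5 − 15.30 = 0.20 up to 15.5 − 15.18 = 0.32.

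**Step 5: check against an outside constant.** Assume a molar mass for glucose of 180.16 g/mol, which the documents do not give. Then f = 18.016, inside the range from Step 1. It returns 130/18.016 = 7.22 and 240/18.016 = 13.32, which round to the protocol's 7.2 and 13.3. It gives 275/18.016 = 15.26, which rounds to 15.3, and 280/18.016 = 15.54, which rounds to 15.5.

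**The case against.** The arithmetic is not in dispute. The case against concerns how much it matters.

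- **mg/dL reads as the governing unit.** The protocol's glucose limits lead with mg/dL, and mmol/L appears only as a bracketed equivalent. On that reading the limit is 275 mg/dL with a slightly wrong conversion beside it. This reduces the ambiguity but does not remove it, because a site working in mmol/L would still apply 15.5.
- **The criterion is not a sharp cut-off.** It asks for persistently high values, gives no number of readings or time window, and applies only after management and dose adjustment have failed. A difference of 1% to 2% is small beside that judgement. This stands.
- **Other rules reach the same patient.** FPG and HbA1c can each trigger withdrawal, investigators may drop a patient at any time, Section 6.2.1.1 starts intervention at FPG above 130 mg/dL, and Table 6-1 calls for dose reduction in persistent grade 3 hyperglycaemia. This stands too. Such a patient would already be under close management.
- **No data consequence.** Section 6.2.1.1 says that the home glucose diary is not collected by the sponsor. This confirms that no analysis is affected. It also means that the sponsor could not readily tell from those readings which limit a site had applied.
- **The mg/dL figures may be rounded as well.** If all three were rounded to the nearest 5 mg/dL, the factor ranges would overlap, at about 17.79 to 17.96. But 275 is a stated threshold, not a measurement, and the overlap excludes 18.016. At that factor even 277.5 mg/dL is only 277.5/18.016 = 15.4 mmol/L.
- **Part of the material could not be read.** Figure 6-1 and part of the amendment history are missing from the text reviewed. That no other place corrects the pair can be said only of the readable text.

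**Conclusion.** The concern holds. The two figures differ by 3.7 to 5.8 mg/dL (0.20 to 0.32 mmol/L), with 15.5 mmol/L the more lenient of the two. The result rests on the protocol's own two FPG pairs, with their mg/dL values taken as exact and their mmol/L values as rounded to one decimal. The assumed molar mass only confirms it.

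This is a minor error. Confidence that the figures do not match is high. Confidence that any patient would be handled differently is low: it would take capillary values that stay inside a band of roughly 5 mg/dL while FPG is below 240 mg/dL and HbA1c is below 10%. The documents give no basis for counting such patients, and the number is likely very small. No endpoint, sample size or analysis depends on the figure.

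**What to change.** State one limit in both units. Either of these is consistent at the factor 18.016:

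- 275 mg/dL (15.3 mmol/L), which keeps the stricter limit and leaves the leading mg/dL figure unchanged.
- 280 mg/dL (15.5 mmol/L), if 15.5 mmol/L was the value intended.

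The choice belongs to the sponsor's clinical team. A short statement that mg/dL governs would settle any remaining rounding difference. The cost is one corrected figure in a clarification letter or the next amendment, with no change to data collection or analysis. Treatment under this protocol version runs to 31 December 2016 at the latest. After that date the correction mainly keeps the record accurate and stops the pair from being carried into later protocols.

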7.1.4 Follow up period

All patients must have a safety evaluation during the Study Completion visit, 28 days after the last dose of study treatment.

A Study Completion CRF page should be completed giving the date and reason for stopping the study treatment.

Patients lost to follow up should be recorded as such on the CRF. For patients who are lost to follow-up, the investigator should show "due diligence" by documenting in the source documents steps taken to contact the patient, e.g., dates of telephone calls, registered letters, etc.

7.2 Assessment types

7.2.1 Efficacy assessments

7.2.1.1 Secondary parameters

7.2.1.1.1 Mean 24-hour urinary free cortisol (UFC)

Screening urinary free cortisol will be measured in three 24-hour urine specimens collected during the screening period (24-h urine collections will have to be performed within the first 8 to 10 days of the screening period so that to have 24h-UFC results available before visit 2). The 24h-UFC concentration results from these three samples will be averaged to obtain the baseline urinary free cortisol level. During the study, mean 24h-UFC will be determined at 4-week intervals until week 24. At week 4, 8, 16 and 20, mean 24h-UFC will be determined from two 24-hour urine collections collected on two consecutive days occurring before the visit. At week 12, 24 and 48, the mean 24h-UFC from three 24-hour urine collections, collected over the week before the visit, will be determined. After week 24, the mean 24h-UFC will be determined at 12-week intervals until end of study visit, from two 24-hour collections during two consecutive days prior to each respective visit (except at Week 48). For each sample, the first urine of the day will be discarded, all subsequent urine has to be collected in the specimen container, including the last urine of the 24-hr period. The urine sample will be checked for volume and creatinine will be measured from the urine sample by the central laboratory.

UFC will be determined by LC/MS/MS. The normal ranges will be determined by the central laboratory's own reference range. All samples, including screening samples, will be analyzed by a central laboratory. Procedures for sample collection, handling, storage and transportation will be provided in detail to the sites by the central laboratory.

7.2.1.1.2 Serum cortisol and plasma ACTH

[figure not shown]
A predose blood draw for plasma ACTH and serum cortisol assessment will be taken. Blood samplings will be done as indicated in [Table 7-1](#). Procedures for sample drawing, handling, storage and transportation will be provided by the central laboratory.

